7.2. Clinical Laboratory

All chemistry, hematology and urinalysis results from the central lab will be summarized into shift tables as normal, non-clinically significant abnormal and clinically significant abnormal. Assessments of clinical significance for abnormal values will be made by the investigator on results that are outside of the normal range or have a toxicity grade of 1 or greater. The shift tables will compare the number and percent of assessments from each visit to baseline values for each treatment group. Abnormal results for each subject will be provided in listings that will include assay name, result, normal range and an explanation for clinically significant values.

Abnormal urine microscopy and manual differential assessments will be listed for each subject.

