5.2. Clinical Laboratory Sampling

Non-fasting samples for clinical laboratory analysis will be collected by a qualified staff member

at the Screening Visit and follow-up visit Weeks 13, 26, 39, and 52 (EOS)/Early Termination. At a minimum, the following tests will be conducted:

- **Chemistry panel:** Albumin, alkaline phosphatase (ALP), alanine aminotransferase (ALT), aspartate aminotransferase (AST), blood urea nitrogen, bicarbonate, calcium (corrected total), chloride, creatinine, glucose, lactate dehydrogenase (LDH), potassium, sodium, bilirubin (total)
- **Hematology:** Hemoglobin, hematocrit, red blood cell (RBC) count, white blood cell (WBC) count with differential, and platelet count
- **Urinalysis:** Clarity, specific gravity, pH, protein, glucose, ketones, nitrite, leukocytes, and occult blood

A urine-based pregnancy test will be performed on female subjects at the Screening Visit and at study visit Day 1, prior to study medication injection.

An HbA1c test will be performed on all subjects at the Screening Visit.

Urine microscopy will be performed if urinalysis values are out of range and the Investigator deems that the microscopy is clinically warranted.

The Investigator or the Investigator's designee must review the results of each subject's Screening Visit clinical laboratory test results prior to the Day 1 visit. The subject must not be randomized on Day 1 if any of the Screening Visit results are outside the normal range for the laboratory AND, in the opinion of the Investigator, are clinically significant.

The results of the clinical laboratory tests will be reported on the laboratory's standard reports. The Investigator must review all laboratory reports in a timely manner, noting "not clinically significant" (NCS) or comment on the clinical significance (clinically significant: yes/no) of any result that is outside the normal range for the laboratory or has a toxicity grade of 1 or greater, then date and initial the report. The Investigator must report all laboratory results that are BOTH outside the normal range for the laboratory or has a toxicity grade of 1 or greater AND, in the opinion of the Investigator, are clinically significant. If any abnormal, clinically significant laboratory measure is found prior to study medication injection, the subject is to be excluded. If it is found after study medication injection, it should be reported as an AE (see [Section 9](#)).

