10.5.3. Safety analysis

Safety assessments will be performed on all subjects who were randomized and received the study medication injection (SM04690 or placebo). Safety assessments include physical examinations, vital signs, clinical laboratory tests, solicitation of AEs and concomitant medications, and general medical evaluations. No formal statistical analyses are planned. Safety will be evaluated based on the incidence, severity, and seriousness of treatment-emergent AEs and by changes in clinical laboratory parameters and vital signs, relative to baseline.

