laboratory abnormalities as Potentially Life Threatening (Grade 4). For example, a low sodium value that falls within a grade 3 parameter (125-129 mE/L) should be recorded as a grade 4 hyponatremia event if the subject had a new seizure associated with the low sodium value.

*** “ULN” is the upper limit of the normal range.

Hematology *	Mild (Grade 1)	Moderate (Grade 2)	Severe (Grade 3)	Potentially Life Threatening (Grade 4)
Hemoglobin (Female) - gm/dL	11.0 – 12.0	9.5 – 10.9	8.0 – 9.4	< 8.0
Hemoglobin (Female) change from baseline value - gm/dL	Any decrease – 1.5	1.6 – 2.0	2.1 – 5.0	> 5.0
Hemoglobin (Male) - gm/dL	12.5 – 13.5	10.5 – 12.4	8.5 – 10.4	< 8.5
Hemoglobin (Male) change from baseline value – gm/dL	Any decrease – 1.5	1.6 – 2.0	2.1 – 5.0	> 5.0
WBC Increase - cell/mm ³	10,800 – 15,000	15,001 – 20,000	20,001 – 25,000	> 25,000
WBC Decrease - cell/mm ³	2,500 – 3,500	1,500 – 2,499	1,000 – 1,499	< 1,000
Lymphocytes Decrease - cell/mm ³	750 – 1,000	500 – 749	250 – 499	< 250
Neutrophils Decrease - cell/mm ³	1,500 – 2,000	1,000 – 1,499	500 – 999	< 500
Eosinophils - cell/mm ³	650 – 1500	1501 - 5000	> 5000	Hypereosinophilic
Platelets Decreased - cell/mm ³	125,000 – 140,000	100,000 – 124,000	25,000 – 99,000	< 25,000
PT – increase by factor (prothrombin time)	1.0 – 1.10 x ULN**	1.11 – 1.20 x ULN	1.21 – 1.25 x ULN	> 1.25 ULN
PTT – increase by factor (partial thromboplastin time)	1.0 – 1.2 x ULN	1.21 – 1.4 x ULN	1.41 – 1.5 x ULN	> 1.5 x ULN
Fibrinogen increase - mg/dL	400 – 500	501 – 600	> 600	--
Fibrinogen decrease - mg/dL	150 – 200	125 – 149	100 – 124	< 100 or associated with gross bleeding or disseminated intravascular coagulation (DIC)

* The laboratory values provided in the tables serve as guidelines and are dependent upon institutional normal parameters. Institutional normal reference ranges should be provided to demonstrate that they are appropriate.

** “ULN” is the upper limit of the normal range.

Urine *	Mild (Grade 1)	Moderate (Grade 2)	Severe (Grade 3)	Potentially Life Threatening (Grade 4)
Protein	Trace	1+	2+	Hospitalization or dialysis
Glucose	Trace	1+	2+	Hospitalization for hyperglycemia
Blood (microscopic) – red blood cells per high power field (rbc/hpf)	1 - 10	11 – 50	> 50 and/or gross blood	Hospitalization or packed red blood cells (PRBC) transfusion

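### SAP 7.2 compares laboratory results between arms only in three-category shift tables; by-arm tables of toxicity grade and numeric change from baseline should be added

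*SAP*

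**What the plan says.** SAP 7.2 states that chemistry, haematology and urinalysis results "will be summarized into shift tables as normal, non-clinically significant abnormal and clinically significant abnormal". The tables count assessments at each visit against baseline, by treatment group. The investigator judges clinical significance for "results that are outside of the normal range or have a toxicity grade of 1 or greater". Protocol 5.2 uses the same trigger: "outside the normal range for the laboratory or has a toxicity grade of 1 or greater". SAP 7.2 also lists abnormal results by subject, with assay, result and normal range. Toxicity grade is not among the fields it names.

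The grades are in Protocol Appendix 2, Table A2. Its haematology part has a row "Hemoglobin (Female) change from baseline value - gm/dL", with a matching row for males, in which grade 1 is "Any decrease – 1.5". A footnote says that the table's values "serve as guidelines and are dependent upon institutional normal parameters".

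Protocol 10.5.3 says that safety is evaluated, among other things, "by changes in clinical laboratory parameters and vital signs, relative to baseline". SAP 7.3 summarises change from baseline at each visit for weight and vital signs. SAP 7.2 has no such line. Under Protocol 5.2, a clinically significant result found after injection is reported as an AE, and SAP 7.1 tabulates TEAEs by toxicity grade and arm.

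**The concern.** The toxicity grade and the numeric value are the two severity measures that do not depend on a site's opinion. Neither is used to compare arms on laboratory results. Within *abnormal*, severity is separated only by the NCS/CS call, which each site's investigator makes result by result. The graded TEAE tables do not make up for this, because a laboratory value reaches them only after the same call.

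An excess of grade 2 or 3 values in one arm that investigators judged NCS would therefore appear in no table as an excess of severity. Counting assessments per visit also leaves out the usual subject-level question of how many subjects per arm reached a given worst grade at any time.

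Haemoglobin has a further weakness. If any decrease counts as grade 1, and grade 1 makes a result abnormal, chance falls within the normal range would fill the haemoglobin NCS cell. The few larger falls would be hard to see among them.

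**Working it through.** The documents state no laboratory abnormality rate, so there is no plan figure to reproduce.

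**1. Grades sharing a cell.** Table A2 grades ALT and AST at 1.1-2.5 x ULN as 1, 2.6-5.0 as 2, 5.1-10 as 3 and above 10 as 4.

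| ALT result | Grade | SAP 7.2 cell if not called CS | In graded TEAE table? |
|---|---|---|---|
| 1.1 x ULN | 1 | NCS abnormal | No |
| 4 x ULN | 2 | NCS abnormal | No |

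The same holds for every analyte that Appendix 2 grades. Only a CS call separates the two results.

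**2. Haemoglobin: inputs from the documents.**
- Grade 1 is any decrease up to 1.5 g/dL, grade 2 is 1.6-2.0, grade 3 is 2.1-5.0 and grade 4 is above 5.0. The steps suggest reporting to 0.1 g/dL.
- Laboratory samples are taken at Screening and Weeks 13, 26, 39 and 52, so there is one scheduled baseline sample and four post-dose results.
- About 445 subjects are randomised 1:1:1:1, and 445/4 = 111 per arm.

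**3. Haemoglobin: assumptions not in the documents.** The visit-to-baseline difference is normal with SD of 0.4-1.0 g/dL, results are rounded to 0.1 g/dL, and there is no true change. An in-range grade 1 fall is tabulated as abnormal.

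**4. Share flagged by chance.** With no drift,

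P(decrease) = 0.5 - 0.5 x P(tie), where P(tie) is about 0.1 x 0.399/SD.

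- SD 0.4: P(tie) = 0.0998, so P = 0.5 - 0.050 = 45.0%.
- SD 1.0: P(tie) = 0.0399, so P = 0.5 - 0.020 = 48.0%.

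A simulation of 400,000 subjects with one shared baseline and four post-dose visits agrees:

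| SD of difference (g/dL) | Any decrease | Grade 1 | Grade 2 or more | Subjects flagged at least once in 4 |
|---|---|---|---|---|
| 0.4 | 45.0% | 45.0% | 0.00% | 75.6% |
| 0.6 | 46.6% | 46.2% | 0.48% | 77.1% |
| 1.0 | 48.0% | 42.0% | 6.04% | 78.2% |

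Per arm and visit this is 111.25 x 0.45 = 50 to 111.25 x 0.48 = 53 subjects. Falls of grade 2 or more are 0.48/46.6 = 1.0% of flagged falls at SD 0.6 and 6.04/48.0 = 12.6% at SD 1.0. The three-category table does not separate them.

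**5. Sensitivity to drift.** P = Phi((-0.05 - drift)/SD).

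| SD | Drift -0.2 | No drift | Drift +0.2 |
|---|---|---|---|
| 0.4 | Phi(0.375) = 64.6% | 45.0% | Phi(-0.625) = 26.6% |
| 1.0 | Phi(0.15) = 56.0% | 48.0% | Phi(-0.25) = 40.1% |

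The range over these cases is about 27-65%.

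**The case against.** The strongest reply is that the plan has more safeguards than the shift tables alone, and much of it stands.

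- A reader might infer that laboratory safety rests wholly on the investigator's opinion. It does not. Range or grade sets the abnormal flag, and the investigator only divides abnormal into NCS and CS. Abnormal results are listed by subject, and CS results become AEs tabulated by grade and arm. What remains is that listings do not compare arms, and the TEAE route passes through the same call.
- A reader might infer that a 0.1 g/dL haemoglobin fall and a fourfold ALT share a cell. SAP 7.2 speaks of shift tables and nowhere says that analytes are pooled. The loss is within each analyte.
- A reader might carry the 45-48% over to laboratory results in general. Haemoglobin is the only Appendix 2 analyte graded on change from baseline. Chance falls also arise equally in the placebo arm, so they add noise and not bias. Nor is the table blind to drift: a mean fall confined to one arm would raise that arm's flagged share. What it loses is severity.
- A shift table is itself a change relative to baseline, and the Protocol synopsis names clinically significant changes as the criterion. SAP 7.2 is therefore not in outright conflict with Protocol 10.5.3. Protocol 10.5.1 also has a general rule to report mean, SD, median and range for continuous variables, but SAP 7.2 does not carry it through, while SAP 7.3 does give numeric change.
- Protocol 5.2 says "If any abnormal, clinically significant laboratory measure is found prior to study medication injection, the subject is to be excluded". The CS baseline row should therefore be nearly empty, which is a consequence of eligibility and not a defect.
- The SAP does not exclude unscheduled results; it is silent on them. Early-termination samples already belong to the Week 52/ET visit.
- SAP 7.2 does not say outright that an in-range grade 1 fall is tabulated as abnormal, and Appendix 2 calls its values guidelines. That reading is the natural one, but it remains a reading.

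**Conclusion.** The concern holds in a limited form. The laboratory comparison between arms loses severity within each analyte, because results of different grade that are called NCS share one cell and no by-arm table of grade or numeric change is planned. This follows from the text and needs no assumption.

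The haemoglobin figure is an illustration. About 45-48% of post-dose results would be flagged by chance under a difference SD of 0.4-1.0 g/dL, 0.1 g/dL reporting, no drift and an in-range grade 1 fall counted as abnormal. With a mean drift of +0.2 to -0.2 g/dL it is about 27-65%. It dilutes the comparison for that analyte alone.

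The documents do not support reading this as a bias between arms or as a failure to capture clinically significant results. It affects descriptive safety reporting and leaves the efficacy analyses untouched. It is a worthwhile, inexpensive improvement.

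**What to change.** In SAP 7.2:

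1. Add, by arm and for each analyte graded in Appendix 2, a shift table from baseline grade to worst post-baseline grade. Count subjects, and use all post-dose results, including unscheduled ones.
2. Add mean (SD) change from baseline per visit for each numeric analyte, as SAP 7.3 does for vital signs.
3. Show the haemoglobin change-from-baseline row separately, by grade, so that grade 2 or more can be read apart from any decrease. If it is merged into a worst-grade table, about 76-78% of subjects would reach at least grade 1 by chance under the assumptions above.
4. State whether an in-range grade 1 result counts as abnormal in the NCS/CS tables.
5. Keep the NCS/CS tables and the listings as supportive.

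The cost is SAP wording and a few extra descriptive tables from data already collected. Visits, sampling and the toxicity scale do not change.

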7.3. Vital Signs

Weight and vital signs, including systolic blood pressure, diastolic blood pressure, pulse rate, respiratory rate and body temperature, will be summarized for each treatment group. A statistical description of each parameter at baseline will be provided along with the change from baseline at each subsequent visit. A subject-level listing will also be provided.

7.4. Concomitant Medications

The World Health Organization Drug Dictionary (WHODD) will be used to classify prior and concomitant medications by Anatomical Main Group (Anatomical Therapeutic Chemical, ATC, Level 1), Therapeutic Subgroup (ATC Level 2), and preferred term. Prior and concomitant medication usage will be summarized by the number and percentage of subjects receiving each medication by treatment group.

Subject-level listings containing prior and concomitant medications (WHODD coding), and procedures and non-drug therapies (MedDRA coding) will be provided.

8. EFFICACY EVALUATION

All efficacy analysis will be performed on the ITT analysis set in support of regulatory requirements. Efficacy analysis will also be performed on the mITT and PP Analysis Sets.

8.1. General Considerations

For continuous variables within each treatment group, the outcome measure at each visit, as well as absolute change (outcome – baseline), will be summarized using descriptive statistics. Categorical variables will be summarized with frequency tables.

Subject-level listings will be provided for each outcome measure in the final analysis report.

8.1.1. ANCOVA Model for Continuous Efficacy Outcomes

ANCOVA models will be used for all continuous efficacy outcome measures summarized by change from baseline in order to test the following three hypotheses:

$$H_0: (\beta_i - \beta_0) = 0$$

$$H_A: (\beta_i - \beta_0) \neq 0, \text{ where } i = 1,2,3$$

In the statement above, β is the least squares estimate in the change in the continuous efficacy outcome from baseline at each timepoint (where β_0 is the estimate for placebo), and i represents each of the three SM04690 treatment groups.

Least squares estimate of difference between each treatment group and placebo in the change in the continuous efficacy outcome from baseline at each timepoint, adjusted for baseline value, will be reported along with unadjusted 95% confidence intervals and P values.

Continuous efficacy measures to be analyzed by the ANCOVA model include:

- WOMAC Pain
- WOMAC Function
- WOMAC Total
- Patient Global Assessment
- Physician Global Assessment
- Medial and Lateral Joint Space Width
- SF-36

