
Statistical methods: A sample size of approximately 445 subjects will be randomized across four treatment groups (0.03 mg active per 2 mL injection: 0.07 mg active per 2 mL injection: 0.23 mg active per 2 mL injection: placebo) based on a 1:1:1:1 ratio. The sample size for this study was based upon accepted statistical practice and not on a formal efficacy hypothesis test and corresponding power analysis.
 
The Safety Analysis Set will comprise all subjects who were randomized and received SM04690 or placebo. The Intent-to-Treat Analysis Set (ITT) will comprise subjects who were randomized. The Modified Intent-to-Treat Analysis Set (mITT) will comprise all randomized subjects who received a protocol specified dose of SM04690 or placebo. The Per Protocol Analysis Set (PP) will comprise ITT subjects who complied with all study procedures and evaluations, and did not have major protocol deviations.
 
The incidence of AEs and proportion of subjects experiencing AEs will be summarized by

seriousness and relatedness to study product for each treatment group; severity of the AEs will be assessed by the Investigator according to the “Guidance for Industry: Toxicity Scale for Healthy Adult and Adolescent Volunteers Enrolled in Preventive Vaccine Trials”. Safety summaries will also include listings of clinical laboratory findings, vital signs, and concomitant medications.

Differences in efficacy outcomes between groups will be estimated at time points using parametric regression methods adjusting for baseline.

TABLE OF CONTENTS

SPONSOR SIGNATURE PAGE	2
PRINCIPAL INVESTIGATOR’S SIGNATURE PAGE.....	3
SYNOPSIS	4
TABLE OF CONTENTS.....	10
LIST OF TABLES.....	13
LIST OF ABBREVIATIONS AND DEFINITIONS OF TERMS.....	14
1. INTRODUCTION	16
1.1. Summary.....	16
1.2. Nonclinical Assessments	16
1.3. Study Rationale.....	16
2. STUDY OBJECTIVES AND PURPOSE	17
2.1. Purpose	17
2.2. Study Objectives.....	17
3. DESCRIPTION OF STUDY DESIGN	18
3.1. Study Endpoints.....	19
3.1.1. Primary Endpoints	19
3.1.2. Secondary Endpoints	19
3.1.3. Exploratory Endpoints.....	19
3.2. Measures to Minimize Bias	20
3.2.1. Blinding	20
3.2.2. Randomization/Assignment to Investigational Product or Placebo	20
3.2.3. Subject Re-screening.....	20
3.2.4. Unblinding During the Study.....	20
3.3. Investigational Product	21
3.3.1. Rationale for Dosages and Dosing Regimen	21
3.3.2. Dosages and Dosing Regimen	22
3.3.3. Dose Modifications.....	22

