5.8. Western Ontario and McMaster Universities Arthritis Index (WOMAC)

The subject will complete the WOMAC Version NR3.1 questionnaire at all visits; at the Day 1 visit, the subject will complete the questionnaire prior to study injection. The WOMAC is a widely-used, proprietary outcome measurement tool used by health professionals to evaluate the condition of patients with OA of the knee and hip, including pain, stiffness, and physical functioning of the joints.

Upon completion of the WOMAC, both the subject and the study staff member will sign/initial and date the source document to indicate that the activity and pain assessments are reported accurately.

The WOMAC questionnaires will be provided by the Sponsor and may not be reproduced.

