2.1. Sample Size

A sample size of approximately 445 subjects will be randomized at a ratio of 1:1:1:1 (0.03 mg active per 2 mL injection : 0.07 mg active per 2 mL injection : 0.23 mg active per 2 mL injection : placebo). The sample size for this study was based upon accepted statistical practice to establish an acceptable level of precision with respect to treatment effect estimation ([Piantadosi 1997](#)).

To explore possible power expected from this study design, an analysis of covariance regression model was simulated via a Monte Carlo simulation of 1000 replicates. The simulation model estimated a change in WOMAC Pain from baseline comparison between SM04690 and placebo adjusting for baseline WOMAC Pain. The following assumptions were made for the power simulation:

- Sample size of 100 subjects per group,
- Type 1 error rate of 5%,
- WOMAC Pain Baseline average is 11 points [scale 0-20] with a standard deviation of 3,
- WOMAC Pain Baseline is the same for both treatment and placebo groups,
- Treatment change from baseline is -5.8 points, leading to a final score of 5.2 points [scale 0-20]
- Historical placebo change from baseline is -3.5 points, leading to a final score of 7.5 points [scale 0-20]
- Final pain score has standard deviation of 4 and is the same for both treatment and placebo groups, and
- Correlation between baseline and final pain score is 0.1.

The WOMAC Pain subscore parameters were based upon observed data from the 0.07 mg group in SM04690-01. Based upon these assumptions, SM04690-OA-02 is estimated to have 95.8% power.

A simulation model for WOMAC Function was also estimated. The following assumptions were made for the power simulation:

- Sample size of 100 subjects per group,
- Type 1 error rate of 5%,
- WOMAC Function Baseline average is 39 points [scale 0-68] with a standard deviation of 11,
- WOMAC Function Baseline is the same for both treatment and placebo groups,
- Treatment change from baseline is -19.5 points, leading to a final score of 19.5 points [scale 0-68]
- Historical placebo change from baseline is -13.5 points, leading to a final score of 25.5 points [scale 0-68]
- Final function score has standard deviation of 15 and is the same for both treatment and placebo groups, and
- Correlation between baseline and final function score is 0.1.

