6.2. Demographic and Baseline Characteristics

Demographic and baseline characteristics, including gender, race, ethnicity, age, weight, height, body mass index (BMI), Kellgren-Lawrence (KL) grade, presence of bilateral OA and

Widespread Pain Index (WPI) score will be summarized by treatment group and listed for individual subjects.

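### The efficacy ANCOVA adjusts only for the outcome's own baseline and leaves out site and the baseline variables already collected: a modest, avoidable loss of precision

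*SAP*

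**What the plan says.** - **Main model.** SAP 8.1.1 reports the dose-versus-placebo difference "in the change in the continuous efficacy outcome from baseline at each timepoint, adjusted for baseline value, will be reported". The protocol synopsis agrees: "parametric regression methods adjusting for baseline". Protocol 10.5.5 specifies ANCOVA and lists no covariates.
- **Planning inputs.** SAP 2.1 assumes "Correlation between baseline and final pain score is 0.1" and "Correlation between baseline and final function score is 0.1". It gives no correlation for Patient Global Assessment or joint space width (JSW).
- **Variables in hand.** SAP 6.2 summarises, among others, "body mass index (BMI), Kellgren-Lawrence (KL) grade, presence of bilateral OA", age and the Widespread Pain Index (WPI). The schedule in Protocol Appendix 1 collects the underlying data at Screening.
- **Where they are modelled.** Only in SAP 8.2.2, as exploratory treatment-by-covariate interactions.
- **Site.** SAP 2.2 stratifies randomisation by site in blocks of 8. Site is not listed in the ANCOVA.
- **Imputation.** SAP 5.2 conditions on treatment group and the outcome's baseline, separately at each timepoint.

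**The concern.** A pre-specified covariate that predicts the outcome narrows the confidence interval at almost no cost when the data already exist. Here the listed model uses one covariate and passes over five others, as well as the factor that defined the randomisation strata.

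The stake is the fixed sequence in SAP 8.2.1. One failure at 0.05 ends confirmatory testing. WOMAC function at Week 13 supplies H4, H5 and H8, and the SAP states 78.5% power for it. Seventeen hypotheses (H5 to H21) follow H4, including every medial JSW test. Small gains in precision are worth most at those steps.

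**Working it through.** **Inputs (SAP 2.1).** "Sample size of 100 subjects per group"; 5% type 1 error, taken as two-sided to match the hypotheses in 8.1.1. Pain: baseline SD 3, final SD 4, difference 7.5 − 5.2 = 2.3. Function: baseline SD 11, final SD 15, difference 25.5 − 19.5 = 6.0. Correlation r = 0.1 for both.

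**1. The plan's own power figures.** Residual SD = final SD × √(1 − r²).
- Pain: 4 × √0.99 = 3.98. Function: 15 × √0.99 = 14.92.
- Noncentrality = difference / (residual SD × √(2/100)): 4.09 for pain, 2.84 for function.
- Noncentral-t power on 197 df: **98.2%** for pain and **80.8%** for function. The SAP states 95.8% and 78.5%.

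The stated figures are not reproduced exactly. That is a separate matter. The comparisons below start from the recomputed values, so both ends stand on the same footing.

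**2. What the planned baseline term achieves.** SD of change = √(SDb² + SDf² − 2r·SDb·SDf), where SDb and SDf are the baseline and final SDs.
- Pain: √(9 + 16 − 2.4) = √22.6 = 4.75. Share of change variance explained: 1 − 15.84/22.6 = 29.9%.
- Function: √(121 + 225 − 33) = √313 = 17.69. Share explained: 1 − 222.75/313 = 28.8%.
- Against an unadjusted analysis of change, the term lifts power from 92.6% to 98.2% (pain) and from 66.5% to 80.8% (function).
- It explains only r² = 1% of the final score. With own baseline in the model, analysing change or final score gives the same treatment estimate, so 3.98 and 14.92, against raw SDs of 4 and 15, are the noise that remains.

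**3. What further covariates could add.** R² is the assumed further share of residual variance explained; residual SD is multiplied by √(1 − R²). Equivalent extra subjects = 445/(1 − R²) − 445.

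| Assumed R² | Function power, n=100 | Pain power, n=100 | Function power, n=111 | Extra subjects |
|---|---|---|---|---|
| 0 | 80.8% | 98.2% | 84.7% | 0 |
| 2% | 81.5% | 98.4% | 85.4% | 9 |
| 5% | 82.7% | 98.7% | 86.4% | 23 |
| 10% | 84.7% | 99.0% | 88.2% | 49 |

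The n=111 column reflects 445/4 ≈ 111 per arm. The table does not charge for the added terms: five useless covariates would inflate the variance by roughly 5/440 = 1.1%.

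**4. Effect on the sequence.** Assume that 0.03 mg has the same function effect as 0.07 mg, with a shared placebo arm (correlation 0.5 between the tests). By normal approximation, H4 and H5 both reach significance with probability about 70% now, and 71%, 73% or 76% at R² of 2%, 5% or 10%.

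**5. Link to SAP 8.2.2.** There the covariate and its interaction are added together, and the likelihood-ratio test compares the result with the original model, which lacks the covariate. Read literally, a two-level factor such as KL grade is tested on 4 df (1 main effect + 3 interactions). With no interaction at all but a main effect explaining 2% or 5% of residual variance (assumed), noncentrality is −445 × ln(1 − R²) = 9.0 or 22.8, and the P<0.10 trigger fires about 77% or 99% of the time.

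**The case against.** The strongest reply is that nothing is broken. Randomisation makes the baseline-only ANCOVA valid, chance imbalance is already reflected in its confidence intervals, the model is pre-specified, and it agrees with the protocol. The benefit rests wholly on assumed R². Even at 10%, pain gains 0.8 points and function 3.9. The Monte Carlo standard error of the SAP's own function simulation is √(0.785 × 0.215/1000) = 1.3 points. At the planned 111 per arm, function power is already 84.7%. All of this stands, and it limits the point to efficiency.

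A reader might infer more than the documents support:
- *That the baseline adjustment does almost nothing.* The 1% applies to final-score variance; for the modelled change it is about 30%.
- *That the 1% applies to every outcome.* SAP 2.1 gives r only for WOMAC pain and function. Patient Global and medial JSW make up 9 of the 21 hypotheses.
- *That the omitted variables are known to be prognostic.* SAP 8.2.2 lists them as possible effect modifiers. Neither document says that they predict outcome.
- *That medial JSW suffers most.* No figure in the documents supports this.

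A reader might also want the Screening score as a covariate, since "The subject will complete the WOMAC Version NR3.1 questionnaire at all visits". It would add little. If both pre-treatment scores correlate 0.1 with the outcome and 0.5 or 0.7 with each other (assumed), joint R² is 2 × 0.01/(1 + 0.5) or 2 × 0.01/(1 + 0.7), a gain of 0.3 or 0.2 percentage points. The scores are also taken under different conditions: Screening allows symptomatic oral treatment, while Day 1 follows 24 hours without pain medication.

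**Conclusion.** The point holds as a modest loss of precision. The listed model omits site and five variables already in hand, and on the SAP's WOMAC inputs nearly all final-score variance remains unexplained. For an assumed further R² of 2% to 10%, function power at 100 per arm rises by 0.8 to 3.9 points and pain power by 0.2 to 0.8. The value lies in the function tests and whatever follows them in the sequence, since pain is already near 98%. These sizes depend on the SAP's effect sizes, SDs and r = 0.1, on two-sided testing, and on R² values that the documents do not supply. At the bottom of the range the gain is barely more than the cost of the extra terms. The wording of the likelihood-ratio comparison in 8.2.2 needs attention whichever covariates are chosen.

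**What to change.** Before unblinding for the Week 26 interim analysis:

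1. In SAP 8.1.1, pre-specify for H1 to H21: arm, outcome baseline, site (small sites pooled by a rule fixed on blinded counts), KL grade, bilateral OA, age, BMI and WPI. If the sponsor prefers to omit any of these, give the reason.
2. Use the same terms in the imputation model of SAP 5.2.
3. Keep the baseline-only ANCOVA as a sensitivity analysis.
4. In SAP 8.2.2, make the comparator the model that already contains the same subgroup main effect, in the same categories, so that the test isolates the interaction. This matters for age, BMI and WPI if they enter 8.1.1 as continuous terms.
5. Do not add the Screening score.

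Cost: SAP wording and a longer model, with no new data. Degrees of freedom fall from 445 − 4 − 1 = 440 to no fewer than 440 − 5 − 39 = 396, taking the maximum of 40 centres without pooling. Most of that is site. At 445/40 ≈ 11 subjects per centre, some sites will hold incomplete blocks, hence the pooling rule.
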